8.2 Analysis Methods

General Methods

FDA Data Standard Guidelines will be followed. Continuous variables will be summarized using the number of observations, number of observations above the limit of quantification (if applicable), mean, standard deviation (SD) median, and range. Categorical variables will be summarized using frequency counts and percentages. Comparison of belnacasan (VX-765/RVT-201/MSR-001) and placebo groups will utilize Poisson regression for counts, Cox proportional hazards regression for time-to-event data and mixed effects models for continuous and categorical data obtained over study days.

8.3 Analysis of Subject Disposition, History, and Baseline Characteristics

Subject disposition, including analysis population allocation, subjects enrolled, completed each period, discontinued, and primary reason for discontinuation, will be summarized using frequency and percentage. Protocol deviations will be summarized using frequency and percentage. Medical history data and prior and concomitant medications will be summarized using frequency and percentage. Subjects' age, height, weight, and baseline disease characteristics will be summarized using descriptive statistics. Gender, race, and other categorical variables will be provided using frequency and percentage.

8.4 Safety & Tolerability Analyses

All safety & tolerability analyses will be performed on the Safety Population. The safety data will be presented in individual listings and summary tables.

Overall safety will be assessed by the number of belnacasan VX-765/RVT-201/MSR-001 dosed subjects experiencing a grade 4 or 5 SAE during the trial. Of 20 subjects enrolled in the belnacasan group, 3 or more developing a grade 4 or 5 SAE probably related to belnacasan would be

considered unlikely due to chance. Therefore, belnacasan will be determined safe if no more than

2 subjects develop a grade 4 or 5 SAE in the belnacasan group probably related to belnacasan.

In terms of stopping rules, should two or more subjects develop a similar Grade 3 SAE that is at

least possibly related to belnacasan or should one or more subjects develop a \geq Grade 4 SAE that

is at least possibly related to belnacasan, the trial will be paused for DSMB safety review.

Primary Endpoint Analysis

Primary endpoints of adverse and serious adverse events (AE/SAE) will be assessed by Poisson

regression for count data. Events will be counted out to 60 days from randomization to belnacasan

or placebo groups. Because some subjects may be followed for less than 60 days, subject follow-

up time will be included in the Poisson regression as the exposure time variable. If counts are not

Poisson-distributed, either over- or under-dispersed, negative binomial regression will be to

analyze AE/SAE events with appropriate adjustment for over/under dispersion. Comparison of

belnacasan vs. placebo will be expressed as the incidence rate ratio (IRR).

Adverse Events

AEs will be coded according to the latest version of the Medical Dictionary for Regulatory

Activities (MedDRA). The intensity/severity of AEs will be graded according to NCI-CTCAE (see

Section 7.3).

TEAEs, AEs leading to study treatment discontinuation, AEs leading to dose interruption, AEs

related to study medication, SAEs, and AEs leading to death will be summarized by system organ

class, preferred term, and study period. A summary of AEs that are CTCAE Grade 3 or higher, as

well as the most frequent preferred terms, will be provided.

If a subject experiences the same adverse events multiple times within a period, then the event will

be counted only once within the period and by greatest severity.

Descriptive statistics will be used to summarize the safety data.

Clinical Laboratory Values

All laboratory test results will be summarized by period together with the change from baseline.

The frequency distribution for low/normal/high or normal/abnormal will be summarized as well.

The denominators for calculating the percentages will be based on the number of subjects with

non-missing values in the Safety Population.

Vital Signs

Vital sign results will be summarized by period, together with the change from baseline.

Physical Examination

Summaries of physical examinations will present frequency distribution of abnormal findings by

body system and period. The denominators for calculating the percentages will be based on the

number of subjects evaluated for a particular body system of each dose level in the Safety

Population.

Electrocardiogram (EKG)

EKG findings will be classified as normal vs abnormal. The number and percentage of each

category will be summarized using frequency table for each period. The denominators for

calculating the percentages will be based on the number of subjects with non-missing values in

each period.

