For this trial we will treat for a maximum of 28 days. Our rationale for this timeframe is that while there is an expectation that the illness lasts up to 12-15 days in those who recover without complication, others will endure a longer duration, and some will experience persistent, new onset or worsening disease related symptoms. A recent study from the Centers for Disease Control and Prevention (https://www.cdc.gov/mmwr/volumes/70/wr/mm7017e3.htm?s cid=mm7017e3 w) found that among 3,171 non-hospitalized adult COVID-19 patients, 69% had one or more outpatient visits 28–180 days after the diagnosis. Two thirds had a visit for a new primary diagnosis, and approximately one third had a new specialist visit. Symptoms potentially related to COVID-19 were common new visit diagnoses. Visits for these symptoms decreased after 60 days but for some patients continued through 120–180 day. Furthermore, some individuals develop sequela that are likely related to post-viral immune dysregulation in the first few months albeit there is little known about this group. Though we are unlikely to learn about the effect of the drug in this latter population we do need to establish safety for a duration that includes the other groups mentioned above.

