3.2 Primary Endpoint

Incidence of Adverse Events and Serious Adverse Events assessed out to day 60.

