Subjects may withdraw voluntarily from participation in the study at any time and for any reason. Subjects may also be withdrawn on the basis of the Investigator's clinical judgment. This study may be terminated at the discretion of MedStar Health or of any regulatory agency for reasons including safety and/or treatment effect.

For enrolled subjects we anticipate that the main reasons for discontinuation of therapy will be either withdrawal of consent for continuation in the study or inability to tolerate the study. Other instances may include patient death, inability to take the study drug from severity of illness or inhospital complexity of illness. Subjective intolerance of the drug from minor side effects or alternatively cessation of COVID-19 related symptoms well ahead of the 28-day schedule may cause patients to want to discontinue the drug. With regards to drug toxicity itself, we anticipate minor symptomatology from adverse effects, such as headache, dizziness, nausea and vomiting, abdominal discomfort and rash (see also 1.4) based on prior human trial experience with the study drug. Should any subject dosed on the study drug experience seizures, which was reported as an

unrelated adverse event in an epilepsy trial, that individual would be subject to discontinuation out of an abundance of caution. Any emergent symptom that has no clear cause will result in a hold on subsequent study drug dosing until protocol assessment by the Study Investigator. The reasons for discontinuation of study drug will be documented clearly. In all cases study protocol monitoring will continue for the entire 60 days of the protocol as long as the subject stays consented.

When a subject withdraws or is withdrawn before completing the study, the date and reason for withdrawal are to be documented. Subjects who withdraw or who are withdrawn prematurely are to attend an early termination, at which time they will complete all assessments as outlined in the Schedule of Events (Table 1); moreover they will be encouraged to stay enrolled so that further safety and outcome information can be collected and analyzed.

In the event that a subject is withdrawn prematurely due to an adverse event or serious adverse event, the adverse event or serious adverse event will be followed until it resolves or stabilizes, or until it is judged by the Investigator to be no longer clinically significant.

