7.10 Serious Adverse Events

Adverse events (AEs) and serious adverse events (SAEs) will be collected from the time the first dose of IP is administered until 28 days after the last dose of IP. Medical occurrences that began prior to the start of study treatment, but after obtaining informed consent will be captured as Medical History/Current Medical Conditions on the CRF. The Investigator or site staff will be responsible for the identification and documentation of events meeting the criteria and definition of an adverse event or serious adverse event, as provided in the study protocol. SAEs assessed as related to study participation (e.g., dosing, protocol mandated procedures, invasive tests, or change in existing therapy) or related to a concomitant medication will also be captured once the subject has taken the first dose of study medication.

In the event of an AE or SAE, it will be the responsibility of the Investigator to review all documentation (e.g., hospital progress notes, laboratory, and diagnostics reports) relative to the event and attempt to establish a diagnosis of the event based on signs, symptoms, and other clinical information. Once the Investigator becomes aware that an SAE has occurred, they are to report the information to MedStar Health within 24 hours and provide an assessment of causality.

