8.6 Handling of Missing Data

Although every effort will be made to obtain complete data, missing values will likely occur when

data are collected longitudinally. Patterns of missingness over time as well missingness with

MOD00008997 IRB Approved 12/23/2021 - 11/9/2022

Version 2.2 12/14/21 Page 51 of 66

respect to demographic and clinical variables will be assessed. For Poisson and Cox regression analyses, all data can be used up to subject dropout time.

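### The single follow-up-time offset in the primary AE model assumes a constant AE rate over 60 days; if the rate falls and follow-up differs by arm, the rate ratio can be biased in either direction

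*Combined protocol and SAP*

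**What the plan says.** The primary endpoint (Section 3.2) is "Incidence of Adverse Events and Serious Adverse Events assessed out to day 60". Section 8.4 analyses the counts by Poisson regression: "Events will be counted out to 60 days from randomization to belnacasan" or placebo. It recognises that some subjects will be followed for less than 60 days and answers with one term, follow-"up time will be included in the Poisson regression as the exposure time variable". The comparison of "belnacasan vs. placebo will be expressed as the incidence rate ratio (IRR"). Negative binomial regression replaces Poisson if the counts are over- or under-dispersed. Section 8.6 adds only this: "For Poisson and Cox regression analyses, all data can be used up to subject dropout time". No period term and no sensitivity analysis is given for this model. Section 8.5 reuses it for secondary event counts over 60 days.

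On AE collection, Sections 7.9 and 7.10 give a different window from Sections 3.2 and 8.4. They run from the first dose "until 28 days after the last dose of IP", which is about day 56 for a subject who completes 28 days of dosing and about day 35 for one who stops at day 7.

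**The concern.** A treatment-only Poisson model with a log follow-up offset compares AEs per person-day. If the AE rate falls over time, a subject who leaves early contributes mostly high-rate days, and the arm that loses more subjects early shows a higher crude rate. The documents give several reasons to expect a falling rate:

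- Section 1.3 expects that the "illness lasts up to 12-15 days in those who recover without complication", and Section 7.8 records events due to the underlying disease.
- Dosing ends at day 28.
- Table 1 has AE contacts on days 1, 4, 7, 10, 14, 21 and 28 (seven), then only on days 42 and 60 (two).
- Scheduled laboratory draws end at day 28, yet Section 7.7 makes every clinically significant laboratory value an AE. Even at constant true risk, ascertainment would fall.

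The rate ratio is the specified comparison for the primary endpoint. A differential loss could make belnacasan look more toxic than it is, or hide toxicity if placebo loses more subjects.

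**Working it through.** **1. The plan's own figures.** The documents give no AE rate, AE timing or dropout rate, so there is no figure on this point to reproduce. The nearest is the detectable rate-ratio difference of over 60% in Section 8.7. With a Wald test on the log ratio, 20 per arm, two-sided 5% and 80% power, the AEs needed per placebo subject are (1.96 + 0.84)² × (1 + 1/IRR) / [20 × (ln IRR)²].
- IRR 1.6: 7.85 × 1.625 / (20 × 0.2209) = 2.89
- IRR 0.4: 7.85 × 3.5 / (20 × 0.8396) = 1.64

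The figure is plausible at about 1.6-2.9 AEs per placebo subject and is not disputed. I use 2-4 AEs per subject below.

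**2. Inputs.** From the documents: 20 per arm, counting to day 60, one offset. Assumed: a share p of AEs by day 14 (60% or 80%) with the rest spread evenly to day 60; losses uniform on days 7-21 and unrelated to a subject's own AE rate; the same AE rate in both arms at every time point.

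**3. Formula.** Let w be the share lost in an arm, m the mean day of loss (14), and F̄ the mean share of 60-day AEs that a lost subject has already had. The expected AEs per person-day are proportional to

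R(w) = [(1 − w) + w·F̄] / [60(1 − w) + m·w],

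and the limiting IRR is R(belnacasan) / R(placebo). At a constant rate F̄ = m/60, so R(w) = 1/60 for every w and the IRR is exactly 1. With equal w it is 1 for any shape.

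**4. Numbers.** Half the losses fall before day 14 (mean day 10.5) and half after (mean day 17.5).
- p = 0.80: F̄ = ½(0.80 × 10.5/14) + ½(0.80 + 0.20 × 3.5/46) = 0.708
- p = 0.60: F̄ = ½(0.60 × 10.5/14) + ½(0.60 + 0.40 × 3.5/46) = 0.540

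| Loss, belnacasan v placebo | p = 0.60 | p = 0.80 |
|---|---|---|
| 20% v 10% | 0.01787 / 0.01722 = 1.04 | 0.01853 / 0.01752 = 1.06 |
| 30% v 5% | 0.01866 / 0.01693 = 1.10 | 0.01975 / 0.01708 = 1.16 |
| equal | 1.00 | 1.00 |

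Reversing the imbalance inverts the ratio: 1/1.156 = 0.865 for 5% v 30% at p = 0.80. Likewise, with 70% of AEs and all losses by day 14, a true IRR of 1.6 reads as 1.39 when placebo loses 30% and belnacasan 5%.

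**5. Rejection rates (simulation, 20 per arm, p = 0.80, nominal 5%).** At 30% v 5% the planned model rejects in about 11-18% of trials for 2-4 AEs per subject; at 20% v 10%, in about 6-9%. With interval terms (days 1-14, 15-28, 29-60) the IRR returns to 1.00 and rejection to about 5%. The simulated rate changes at the model's own cut points, which favours the correction somewhat.

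**6. Negative binomial.** With 70% of AEs by day 14, losses at day 14, 30% v 5% and a frailty variance of 0.5, about 600 runs gave a median IRR of 1.27 and about 11% rejection. Part of that is small-sample inflation. The fallback addresses dispersion and does not remove the bias.

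**7. The two AE windows.** Suppose 30% v 5% stop drug at day 7, all stay in follow-up, and AEs are collected only to 28 days after the last dose (day 35 or day 56).
- Constant rate, exposure entered as 60 study days: (0.70 × 56 + 0.30 × 35) / (0.95 × 56 + 0.05 × 35) = 49.7 / 54.95 = 0.90
- 70% of AEs by day 14 and 90% by day 28: 0.98 with 60 study days as exposure, 1.09 with the collection window as exposure

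The definition of exposure therefore changes the result even when nobody leaves the study.

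**The case against.** Five points weigh against this, and most of them stand.

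**Stopping drug is not leaving the study.** Section 5.3 says that "cessation of COVID-19 related symptoms well ahead of the 28-day schedule may cause patients to want to discontinue the drug". A reader might infer that subjects will leave once well and that an effective drug will therefore look toxic. The documents do not support that step: Sections 5.3, 7.2 and 8.1 keep subjects who stop drug under observation to day 60 while they remain consented. Only consent withdrawal, loss to follow-up or death shortens follow-up. Section 5.3 foresees consent withdrawal and death but gives no rate and no difference between arms. What remains is that stopping drug may shorten AE ascertainment under Sections 7.9 and 7.10.

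**Early clustering is not documented.** No AE timing is given, and Section 1.3 also expects longer, persistent or new-onset symptoms in some subjects. A falling rate is a reasonable inference, not a stated fact. With AEs spread evenly over 28 days, the ratio at 30% v 5% is about 1.09.

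**The larger figures need a large imbalance.** In arms of 20, 30% v 5% is six subjects v one. At 20% v 10% the shift is small beside a standard error of log IRR of about 0.23 at 2 AEs per subject.

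**Not every early exit fits the null.** A death is itself an SAE, and withdrawal for intolerance reflects AEs. Such cases are not the identical-rate situation computed above.

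**The safety conclusion does not use the ratio.** Section 8.4 calls belnacasan safe if no more than 2 subjects have a probably related grade 4 or 5 SAE. The trial is described as hypothesis-generating and no rejection rule is set for the IRR. AE summaries by study period and a disposition table are already planned, so an imbalance would be visible, though only descriptively.

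**Conclusion.** The point holds as a conditional weakness. The model is unbiased under unequal follow-up only at a constant AE rate; the design makes that unlikely, and neither the negative binomial fallback nor Section 8.6 addresses it. The effect is modest for moderate imbalance and material only for a large one, and its direction follows whichever arm loses more subjects. These sizes rest on the assumed AE timing, loss pattern and AE counts.

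A reader might go further and conclude that the plan will produce a false safety difference. That is not supported: no differential loss is predicted, equal loss gives no bias in the ratio, and the grade 4/5 SAE rule stands apart. The unreconciled AE windows are the better-documented problem, because they leave exposure time undefined whatever the dropout. Overall this is an inexpensive improvement to the primary-endpoint comparison, worth making before unblinding.

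**What to change.** In Section 8.4, and by reference for the 60-day counts in Section 8.5:

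1. Reconcile day 60 (Sections 3.2 and 8.4) with 28 days after the last dose (Sections 7.9 and 7.10), and define exposure as the time a subject was under AE ascertainment. This comes first, because the days 29-60 offset depends on it.
2. Split each subject's exposure at days 14 and 28. Fit the Poisson or negative binomial model to the split records with an interval term, log interval time as offset and a subject-clustered variance. Report the common IRR.
3. Tabulate follow-up time by arm.

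The cost is a few sentences, a few lines of code and two nuisance parameters. Onset dates are already recorded under Section 7.8. The change does not correct dropout that is informative within an interval, so the table of follow-up by arm, read with the reasons for discontinuation, is still needed.

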 - o from randomization to the first day of achieving sustained (i.e., at least 2 days) resolution of fever for subjects who presented with fever at any point between enrollment and day 2 post randomization

- with temperature <38C or >=38C experienced in total during the first 28 days post randomization
- o from randomization to the first day post randomization of achieving oxygenation of SpO2>=96% in room air when resting for subjects who presented with SpO2>93% and <96% in room air, when resting, at enrollment
- o with oxygenation of SpO2>= 96% or SpO2>93% in room air, when resting, in total during the first 28 days post randomization

3. COVID-19 related deterioration and mortality

- **3a. Deterioration and mortality rates:** Proportion of treatment group, versus placebo group, respectively, who per subject reporting or medical records by day 14, day 28 and by day 60 post randomization had experienced:
 - o an emergency department visit, other than at study enrollment or study visits
 - hospitalization for COVID-19
 - o hospitalization for COVID-19 requiring oxygen
 - hospitalization for COVID-19 requiring ICU
 - o hospitalization for COVID-19 requiring ventilation
 - o COVID-19 related death
 - death
 - hospitalization or death
- **3b.** *Time to and length of deterioration*: Comparison of treatment group versus placebo group, respectively, in the number of days
 - o from randomization until the first day of experiencing hospitalization for COVID-19
 - o of hospitalization for COVID-19 experienced in total by day 14, by day 28 and by day 60 post randomization
 - o of hospitalization for COVID-19 requiring oxygen experienced in total by day 14, by day 28 and by day 60 post randomization
 - of hospitalization for COVID-19 requiring ICU experienced in total by day 14, by day 28 and by day 60 post randomization
 - o of hospitalization for COVID-19 requiring ventilation experienced in total by day 14, by day 28 and by day 60 post randomization

4. WHO 9-Point Ordinal Scale

- 0. Uninfected or "no clinical or virological evidence of infection"
 - a. defined as subject answering "Yes" to "In the past 24 hours, have you returned to your usual health (before your COVID-19 illness)?"
- 1. Not hospitalized, no limitations on activities
 - a. defined as subject answering "Yes" to "In the past 24 hours, have you returned to your usual activities (before your COVID-19 illness)?"
- 2. Not hospitalized, limitation on activities

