7.7 Laboratory Abnormalities

Clinical labs will be performed locally at WHC or other MedStar clinical sites. Labs to be drawn during the study include serum chemistries, a hematology panel and an immune panel (see Appendix 12.1 for more details). A serum pregnancy test must be performed, and the result must be negative prior to the entry of women of child-bearing potential.

Clinical laboratory reports must be reviewed by a physician for out-of-range values within 12 hours of receipt. Out-of-range values will be evaluated using the following notations:

- NCS: Not clinically significant
- LE: Laboratory Error
- PT: Subject abnormal; relates to the subject's usual state of health
- CS: Clinically Significant. This value cannot be explained by any of the other indicators.

By definition a lab value flagged as "CS" indicates an adverse event and will be captured on the CRF. A laboratory test flagged "CS" should be repeated as soon as possible, then the Investigator should use his or her judgment as to whether the abnormal finding is sufficient reason to immediately withdraw the subject from the study.

If a laboratory value is considered to be serious and life-threatening and at least possibly related to the study drug, the subject should be immediately discontinued from the study and appropriate therapy started. Refer to Sections 7.8 to Section 7.13 for definition of a serious adverse event and related terms, and details on reporting a serious adverse event.

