8.5 Treatment Effect Analyses

Secondary Endpoint Analyses

Event counts over 60 days will be analyzed by Poisson regression as described above in 8.4. Time

to events will be analyzed by Cox regression. Differences between belnacasan and placebo with

respect to change in continuous endpoints will be assessed by mixed effects models for continuous

repeated measures data and mixed effects logistic models for repeated categorical variables.

Endpoint proportions of belnacasan and placebo groups will be assessed by contingency table

analysis (chi-square).

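### Section 8.4 sends under-dispersed AE/SAE counts to negative binomial regression, which cannot model them, and gives no rule for an arm with no SAE

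*Combined protocol and SAP*

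**What the plan says.** Section 8.4 (Primary Endpoint Analysis) compares AE/SAE counts to day 60 by Poisson regression, with follow-up time as exposure. Its fallback for counts that do not fit reads "Poisson-distributed, either over- or under-dispersed, negative binomial regression will be to" and continues "analyze AE/SAE events with appropriate adjustment for over/under dispersion". No adjustment, dispersion test or threshold is named. The comparison of "belnacasan vs. placebo will be expressed as the incidence rate ratio (IRR").

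Section 8.5 carries this over: "Event counts over 60 days will be analyzed by Poisson regression as described above in 8.4". Section 8.2 is more general: "Comparison of belnacasan (VX-765/RVT-201/MSR-001) and placebo groups will utilize Poisson regression for counts".

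In Section 3.4, endpoint 2b compares the number of days "with temperature <38C or >=38C experienced in total during the first 28 days post randomization", and likewise days "with oxygenation of SpO2>= 96% or SpO2>93% in room air, when resting, in total during the first 28 days post randomization". No section says which model these totals get.

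Section 8.6 covers the Poisson model only for dropout. Sections 8.4 to 8.6 do not say what is reported if an arm has no SAE. Section 8.4 does plan individual listings, summary tables and descriptive statistics.

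**The concern.** The fallback names one model for both directions of misfit, and that model works in only one. Under-dispersion leaves the rate ratio itself alone, but an unscaled interval around it is too wide.

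Under-dispersion is possible here. If each subject has at most one SAE, the variance/mean ratio is 1 − p. The rule in Section 8.4 that counts a repeated event once per period would push the same way if it were applied to the modelled counts.

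The trial exists to estimate an effect size for a larger study (Section 8.7), so the reported rate ratios and intervals matter more than any single p-value. With few SAEs expected, an empty arm is also a realistic outcome, and the planned rate ratio then has no usable Wald interval.

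**Working it through.** **Inputs.** From the documents: 20 subjects per arm (8.7), counts to day 60 (8.4), totals over 28 days (3.4, endpoint 2b). The documents give no AE rate, SAE rate, dispersion or expected febrile days, so those below are assumptions. Simulated figures use 20,000 trials per case, equal follow-up and nominal two-sided 5%. NB means negative binomial with no further adjustment.

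**The plan's own figure.** Section 8.7 says a difference in rate ratios of over 60% is needed for 80% power. With no baseline rate this cannot be reproduced. A ratio of 0.4 would need a control mean of (1.960 + 0.842)² × (1 + 1/0.4)/20 ÷ (ln 0.4)² = 7.85 × 0.175 ÷ 0.840 = 1.64 events per subject. It says nothing about dispersion.

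**1. The model limit.** NB variance is μ + kμ² with k ≥ 0, so it is never below μ. In 1000 simulated data sets with clear under-dispersion, the NB likelihood was highest at k = 0 in all of them, which is the Poisson fit.

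**2. AE counts.** Assume 20 possible AE terms, each with probability 0.10 (mean 2). Variance/mean = (1 − p)(1 + (n − 1)ρ), where ρ is within-subject correlation.
- At ρ = 0 it is 0.90. Poisson SE of the log ratio under the null: √(2/40) = 0.224. True SE: 0.224 × √0.90 = 0.212, a ratio of 1.05 (simulated NB: 1.06).
- False positives: NB about 3%, quasi-Poisson 4 to 5%.
- Ratio 1.5 (p = 0.10 v 0.15): ln 1.5 = 0.405; Poisson SE √(1/40 + 1/60) = 0.204; true SE √(0.90/40 + 0.85/60) = 0.191. Power ≈ Φ((0.405 − 1.96 × 0.204)/0.191) = 51%. Simulated: NB 51%, quasi-Poisson 55%.
- Break-even: ρ = p/((1 − p)(n − 1)) = 0.1/(0.9 × 19) = 0.006. Above this the counts are over-dispersed. At ρ = 0.05, 0.90 × 1.95 = 1.755; NB then rejects 6.1% of true nulls and quasi-Poisson 4.8%.

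**3. Endpoint 2b, if its totals are treated as counts.** With complete diaries, days below 38C = 28 − F, where F is febrile days. The total is under-dispersed unless SD(F) exceeds √(28 − E(F)), which is 5.2, 5.0 and 4.8 days at mean 1, 3 and 5.
- Assume F is negative binomial with k = 1. At mean 3, Var(F) = 3 + 9 = 12, so variance/mean = 12/25 = 0.48. NB then rejects 0.7% of true nulls.
- Mean febrile days 3 v 1 give 25 v 27 days below 38C. ln(27/25) = 0.077; Poisson SE √(1/500 + 1/540) = 0.062; true SE √(12/(20 × 625) + 2/(20 × 729)) = 0.033. Power ≈ Φ((0.077 − 1.96 × 0.062)/0.033) = 9%.
- Febrile days from the same diaries: ln 3 = 1.099; NB SE √((1/3 + 1)/20 + (1 + 1)/20) = 0.408; z = 2.69.

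| Simulated power | NB | Quasi-Poisson |
|---|---|---|
| Days <38C, febrile means 3 v 1 (k = 1) | 9% | 69% |
| Days ≥38C, same diaries | 79% | 73% |
| Days <38C, febrile means 4 v 2 (k = 0.5) | 12% | 61% |
| Days ≥38C, same diaries | 67% | 62% |

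**4. An arm with no SAE.** At λ SAEs per subject, an arm is empty with probability q = exp(−20λ). At least one arm is empty with probability 1 − (1 − q)², and both with q².

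| λ | q | At least one empty | Both empty |
|---|---|---|---|
| 0.05 | 0.368 | 60% | 14% |
| 0.1 | 0.135 | 25% | 2% |
| 0.2 | 0.018 | 4% | 0.03% |

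A Poisson fit to 0 v 2 SAEs returned a rate ratio near 7 × 10⁸, an SE near 11,000 and a Wald p of 0.999. An exact comparison of proportions stays defined: 3 v 0 subjects gives a difference of 15 points, 95% interval about −3 to +37.5. For 0 of 20 the upper limit is 1 − 0.025^(1/20) = 16.8%.

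**The case against.** Five points can fairly be made for the plan.

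- **The adjustment clause may cover it.** Pearson scaling of a fit that has fallen to k = 0 gives the quasi-Poisson standard error, and the text permits that reading. This stands in part: the NB figures above are for unadjusted NB. A pre-specified analysis should still name the adjustment, and the clause does not make NB fit under-dispersed counts.
- **AE counts are more likely over-dispersed.** The AE definition is broad (a laboratory value flagged clinically significant "indicates an adverse event and will be captured on the CRF"), and very little within-subject correlation reverses the problem. This stands. A reader might infer that the rule could hide an AE excess; about 4 points of power, in a trial that says it is probably under-powered, do not support that.
- **Endpoint 2b is not clearly under this rule.** Section 8.5 speaks of event counts over 60 days, whereas 2b totals diary days over 28. Daily fever status could go to the mixed effects logistic model, although that compares daily odds and not totals. This stands: for 2b the defect is an unassigned method, and the large power loss is conditional.
- **The two temperature totals cannot contradict each other.** A reader might infer from 9% and 79% that one diary gives opposite answers. With complete diaries the totals sum to 28, so both favour the same arm; only the power differs.
- **An empty arm would still be reported** through the planned listings and tables. True, but those do not supply the promised comparison.

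**Conclusion.** The rule in Section 8.4 is wrong as written for under-dispersed counts and should be corrected, but its likely effect on the primary AE comparison is small and conservative. The figures rest on the assumed 20-term, zero-correlation case. The estimated rate ratio does not change.

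A reader might infer that the safety conclusion is compromised. The documents do not support that: the 2-of-20 criterion and the pause for DSMB review count subjects and do not use the rate ratio, and the trial is described as hypothesis generating.

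The larger effect, about 9% against 69% power, arises only if the endpoint 2b totals are analysed as counts under the present rule, and only under the assumed fever distribution.

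The missing rule for an empty arm is a real secondary gap. How often it would bite depends wholly on the SAE rate, which the documents do not give.

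**What to change.** **Section 8.4, dispersion.** Limit negative binomial regression to over-dispersed counts. State that under-dispersed counts use Poisson regression with Pearson-scaled (quasi-Poisson) or robust standard errors and the same follow-up offset, and state how dispersion will be judged. Quasi-Poisson throughout is an acceptable alternative. It has no likelihood (no likelihood-ratio test or AIC) and loses some power when counts are over-dispersed: 73% v 79% in the febrile-day case above, part of which reflects NB's own inflated error.

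**Section 8.5.** Let secondary event counts inherit the corrected rule, and name the method for the 28-day totals in endpoint 2b. If they are counts, use the scaled model with log diary days observed as offset.

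**Empty arm.** Add that, if an arm has no SAE, the difference in the proportion of subjects with at least one SAE is reported with an exact interval and person-days per arm beside it. If both arms are empty, give each arm's exact upper limit. This is a fallback to the planned rate ratio, not a replacement.

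**Cost.** Minor analysis work in standard software and no extra patients. The exact interval is conservative when SAEs are rare (2.8% to 3.7% false positives at 0.1 per subject), and it ignores repeat events and unequal follow-up.
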